4.5.5 Physical examination

No separate summaries of physical examination findings will be produced since there are no physical examination results reported outside of AE reporting.

4.6 Efficacy

4.6.1 Secondary endpoint (first efficacy endpoint)

The primary analysis of the secondary endpoint (AAER over 104 weeks) will quantify the effect of the initially randomised treatment, regardless of the treatments that subjects actually received, or whether the subjects received other controller therapy/rescue medications post IP discontinuation based on the hypothetical scenario that other biologic treatments are not available. This approach assumes that the response after start of another biologic that impacts asthma control is different from the response for subjects who complete their randomised treatment. A hypothetical strategy will be used which will include all available data after treatment discontinuation in the planned treatment period but only up until the initiation of another biologic that impacts asthma control treatment. Subjects will be encouraged to continue to undergo applicable study related visits/procedures for the full 104-week period even after premature discontinuation of IP. Consequently, subjects lost to follow-up, subjects who die, subjects who withdraw their consent, those who do not enrol into the LTE study, and those who start another biologic that impacts asthma control will be the sources of missing information for the primary analysis. Missing data from premature study withdrawal will be modelled based on what was observed during the study using direct likelihood approaches, which is a valid approach under the assumption that data are missing at random (MAR).

AAER in the tezepelumab group will be compared to that seen in the placebo group using a negative binomial model. This model will be used to estimate the treatment effect and 95% confidence intervals. Analysis will be performed for the FAS comparing the Randomised Tezepelumab treatment group with the Randomised Placebo treatment group.

The response variable in the model will be the number of asthma exacerbations experienced by a subject over the 104-week planned treatment period (or shorter duration if not followed up for the full 104 weeks). Treatment, region and history of exacerbations (<=2 or >2 in

previous 12 months) will be included as factors in this model. For study D5180C00007, age at screening (adolescents or adults) will also be included in the model. The logarithm of the time at risk (in years) for exacerbation will be used as an offset variable in the model, to adjust for subjects having different follow-up times during which the events occur. Time during an exacerbation and the 7 days following an exacerbation in which a new exacerbation cannot occur, will not be included in the calculation of time at risk for exacerbation. For all further endpoint derivation details, see Section 3.3.1.1.

Descriptive summaries of the asthma exacerbations will also be presented. Unadjusted exacerbation rates will be summarised using an approach weighted by subject's time at risk (i.e., the total number of exacerbations for each treatment divided by the total time at risk for that treatment). Asthma exacerbation information will also be listed for the FAS-LTE analysis set. Subjects with a delay between the predecessor study EOT visit and the enrolment visit in the LTE study will be highlighted with an asterisk in the exacerbation listings.

Adjusted (model-based) exacerbation rates will be presented using the marginal rates approach described in Bartlett, 2018.

The following sensitivity analyses may be conducted.

Controlled imputation

To examine the sensitivity of the results of the primary analysis to departures from the underlying assumptions about missing data, controlled multiple imputation analyses may be performed which allow for different underlying assumptions to be used.

An underlying negative binomial stochastic process for the number of exacerbations will be assumed and post-study withdrawal counts will be imputed conditional upon the observed number of events prior to the withdrawal under both missing at random (MAR) and missing not at random (MNAR)/dropout reason-based multiple imputation (DRMI) assumptions respectively:

MAR: Missing counts in each arm will be imputed assuming the estimated event rate within that treatment group.

MNAR/DRMI: Missing counts will be imputed differently depending on the reason for dropout;

Missing counts for subjects in the tezepelumab arm at the time of the dropout who dropped out for a treatment-related reason will be imputed based on the estimated event rate in the placebo arm (the "copy reference" approach), whereas the remaining subjects who dropped out will be imputed assuming MAR.

Error! Reference source not found. Table 6 Treatment arms for imputation of tezepelumab subjects under DRMIsummarises how tezepelumab subjects withdrawing from study will be handled in the DRMI analyses described above. The rules in the table will be

applied irrespective of the length of time between discontinuing IP and withdrawing from the study (noting that the treatment policy strategy is used for these sensitivity analyses

Table 6 Treatment arms for imputation of tezepelumab subjects under DRMI

| Reason for withdrawing from study | Reason for discontinuing IP | DRMI |
|---|--|--|
| Death | | Placebo |
| Site terminated by sponsor | | Tezepelumab |
| Study terminated by sponsor | | Tezepelumab |
| | Death | Placebo |
| | Adverse event | Placebo |
| | Development of study-specific discontinuation criteria | Placebo |
| | Severe non-compliance to protocol | Placebo |
| Loss to follow-up Withdrawal by subject Withdrawal by parent/guardian Other | Subject lost to follow-up | Placebo by default (pending blinded review of any further information) |
| Oulei | Subject decision | Placebo by default (pending blinded review of any further information) |
| | Other | Placebo by default (pending blinded review of any further information) |

A blinded review of subjects who discontinued IP for reasons of "Subject lost to follow-up", "Subject decision" or "Other" will be performed prior to unblinding at the primary database lock. A listing of these subjects and the assumptions made under DRMI will be documented. If any recorded comments (on either of the "Discontinuation of Investigational Product" or "Disposition" eCRF pages) indicate clearly that the reason for study withdrawal was not related to treatment, then the "Placebo" default for DRMI in the above table may be changed for that subject.

The methodology used for sensitivity analysis is described in more detail in Keene et al., 2014. The steps for carrying out multiple imputation are outlined below.

Step 1: Fitting a negative binomial model to the observed data

A negative binomial regression model will be fitted to the observed exacerbation data with treatment group, region, age and history of exacerbations included as covariates. The logarithm of the time at risk (in years) for exacerbation will be used as an offset variable in the model.

Step 2: Drawing samples from the posterior distribution

The negative binomial distribution is conventionally defined as the probability distribution of the number of successes Y before k failures are seen in a series of independent Bernoulli trials with probability p of success and (1-p) of failure.

The posterior distribution for parameter k and coefficients β will be created as a product of non-informative prior and the likelihood from the model in Step 1. A uniform prior distribution will be assumed for the regression coefficients. A Gamma (10^{-4} , 10^{-4}) will be assumed for 1/k.

With the use of Markov Chain Monte Carlo (MCMC) method, 100 samples of k and β will be drawn from their posterior distribution. Convergence of the MCMC algorithm will be assessed.

A random seed of 991511 will be used. The first 2000 iterations will be discarded to allow for convergence to a stationary distribution and to remove the effect of the starting values ("burn-in"). A gap of 100 iterations will be used between imputations to ensure independence between imputations ("thinning").

Step 3: Imputing missing data

For a subject who withdrew from the study early, let Y_1 denote the number of events prior to withdrawal (over time t_1), and let Y_2 denote the number of unobserved events after withdrawal until the end of the study's planned treatment period (over time t_2). For a subject who completes the planned treatment period, Y_1 denotes the number of events prior to completion (over time t_1). Using the formula in Keene et al., 2014, the unobserved events Y_2 will be imputed from a negative binomial distribution with parameters k^* and p^* , where:

$$k^* = k + Y_1$$

$$p^* = (k + \varphi_1) / (k + \varphi_1 + \varphi_2)$$

 φ_1 is the expected number of events prior to withdrawal

 φ_2 is the expected number of events after withdrawal

Thus, Y_1+Y_2 gives the number of exacerbations (observed and imputed) over the planned treatment period, t_1+t_2 . A random seed of 112358 will be used for the imputation.

The parameters φ_1 and φ_2 will be derived for each set of β and k parameters sampled in Step 2 under 2 different missing data scenarios, MAR and DRMI.

Step 4: Multiple imputation algorithm

For each scenario detailed in Step 3, the algorithm for implementing multiple imputation is:

Select the first set of parameters $(\hat{\beta}, \hat{k})$ from Step 2

Impute Y_2 for each subject who discontinued from the study early, using the method outlined in Step 3

Calculate $Y_3 = Y_1 + Y_2$ for all subjects, where $Y_2 = 0$ for subjects who completed the study and $Y_2 \ge 0$ for subjects who discontinued from the study early.

A negative binomial regression model will be fitted using Y_3 as the response variable with treatment group, region, age and history of exacerbations included as covariates. For subjects completing the planned treatment period, the offset will be the logarithm of the time at risk (in years) for exacerbation. For subjects with an imputed number of exacerbations after withdrawal, the offset will be the logarithm of the study's planned treatment period excluding the time during an observed observation and the 7 days following an observed exacerbation.

Using the model from (iv) calculate treatment differences for the comparisons of interest

Select the next set of parameters $(\hat{\beta}, \hat{k})$ from Step 2 and repeat (ii) through to (v) a further 99 times.

Using Rubin's formulae, summarise the sets of treatment differences in (v) to give an overall treatment difference for the comparisons of interest with 95% confidence limits. The number of events and total time at risk will be derived by taking the arithmetic mean of these values across the sets of data.

Back-transform the estimates and 95% confidence limits to give a rate ratio and corresponding limits

4.6.1.1 Supportive analysis

The analysis described above in Section 4.6.1 will be repeated based on the FAS-LTE comparing Tezepelumab Predecessor+Tezepelumab LTE with Placebo Predecessor+Placebo LTE. Descriptive statistics of the asthma exacerbations will be provided overall (Week 0 to Week 104).

[figure not shown]
4.6.1.2 Durability of benefit during the treatment period

Durability of benefit will be explored for the FAS-LTE analysis set. Exacerbations rates will be presented for the predecessor period and LTE period separately for the Tezepelumab Predecessor+Tezepelumab LTE and Placebo Predecessor+Placebo LTE treatment groups, as well as the Placebo Predecessor+Tezepelumab LTE treatment group. Time at risk during the predecessor and LTE period should be used accordingly.

[figure not shown]
4.6.1.3 Subgroup analyses

[figure not shown]
The AAER negative binomial model will also be provided by subgroups as defined in Section 3.1.8 for the planned-treatment period for the FAS analysis sets for study D5180C000007 only. A model similar to the one described in Section 4.1.6 will be used with the addition of a covariate for the interaction term between treatment and subgroup.

[figure not shown]

[figure not shown]

[figure not shown]

5 INTERIM ANALYSES

No interim analyses are planned in this trial.

An independent Data and Safety Monitoring Board (DSMB) will safeguard the interests of adolescent subjects by assessing the safety of the intervention. The DSMB will review safety data on a regular basis as set out in a DSMB charter. The data for review will be outlined in a DSMB charter. The DSMB will have access to individual treatment codes and will be able to merge these with the collected study data whilst the study is ongoing. For reference, the DSMB will also have access to study data from adults.

The personnel involved in the clinical study at AstraZeneca will remain blinded to these analyses and will have no knowledge of the results presented to the DSMB.

6 CHANGES OF ANALYSIS FROM PROTOCOL

• A new analysis set "LTE analysis set" has been added to the SAP to show the full disposition of subjects from the predecessor studies, and to allow for the possibility that subjects may be enrolled or randomised in the LTE study but do not take IP in the LTE study.

8 APPENDIX

8.1 Adverse events of special interest

For adverse events of special interest (AESIs) summarised in sections 8.1.1, 8.1.4, 8.1.8, and 8.1.9, AESIs and related definitions based on MedDRA terms are not included in this SAP to facilitate their maintenance (e.g., management of MedDRA version changes), and for convenience in using them directly in SAS programming. These detailed definitions will be finalised by the study team prior to the primary database lock and provided together with the study datasets at the time of submission.

8.1.1 Anaphylactic reactions

Potential anaphylactic reactions will be defined on the basis of Sampson's criteria (see Sampson et al., 2006). These will be identified using a modified Standardized MedDRA Query (SMQ), with additional constraints on the timing of the AE onset date relative to the timing of the injection.

Confirmed anaphylactic reactions will be those defined following medical review of the preferred terms identified as potential anaphylactic reactions, as well as any relevant supporting data.

8.1.2 Immune complex disease (Type III hypersensitivity reactions)

Immune complex disease will be defined using a single PT of "Type III immune complex mediated reaction". Since this will already be covered by the general AE reporting by SOC/PT, separate summary tables will not be needed for this AESI.

8.1.3 Hypersensitivity reactions

Hypersensitivity reactions will be defined on the basis of an SMQ: Hypersensitivity (narrow). All hypersensitivity reactions (serious plus non-serious) as well as serious hypersensitivity reactions will be summarised.

8.1.4 Malignancy

Malignancy will be defined on the basis of an SMQ: Malignant or Unspecified Tumors Non-haematological malignant tumours; (narrow), Haematological tumours of unspecified malignancy; (narrow), Non-haematological tumours of unspecified malignancy; (narrow), Haematological malignant tumours; (narrow).

8.1.5 Helminth infections

Helminth infection will use an investigator-driven definition, i.e., will be directly determined from what is entered on the eCRF.

A subject will be considered to have this AESI if the subject has at least one preferred term where the dedicated Helminth Infection eCRF page was also completed for that event (linked by AE number), with AE onset date during the relevant study period for analysis.

8.1.6 Severe infections (as defined in the protocol)

Severe infections will use an investigator-driven definition, i.e. will be directly determined from what is entered on the eCRF.

A subject will be considered to have this AESI if the subject has at least one preferred term with AE onset date during the relevant study period for analysis, which satisfies the following:

"AE Category" on Adverse Events eCRF page marked as "Severe Infection", and one or more of the following:

- AE is serious ("Serious" on Adverse Events eCRF page marked as "Yes"), or
- AE required treatment with systemic antiviral medications, intravenous antibiotics or medications for Helminth parasitic infection, or
- AE resulted in permanent discontinuation of study drug ("Action taken, investigational product" on Adverse Events eCRF page marked as "Drug permanently discontinued").

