### 2.3 Benefit/risk assessment

In order to evaluate the clinical benefit-risk balance for tezepelumab, preclinical and clinical data have been taken into consideration, as well as a review of the available information for monoclonal antibodies that are approved for and are in development for the treatment of severe asthma. Benefits for tezepelumab over placebo include a clinically meaningful reduction in asthma exacerbations, improvement in lung function and asthma control metrics.

Tezepelumab - D5180C00018

Tezepelumab has been well tolerated with no safety signals identified in studies to date. No serious allergic reactions or anaphylactic reactions considered related to tezepelumab were reported in the Phase 2 program. Although TSLP suppression could theoretically have unanticipated immune-related side effects impairing host defense against certain infections, there is no clear preclinical or clinical evidence supporting such a role, and no safety signals related to infections have been detected in the tezepelumab program.

The benefit/risk assessment for tezepelumab in severe asthma based on the development through Phase 2 is favourable. The benefit / risk assessment will be further defined by results from the Phase 3 program.

More detailed information about the known and expected benefits and risks and reasonably expected adverse events of tezepelumab may be found in the Investigator's Brochure.

See Section 8.4.6 for information regarding the DSMB.

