### **8.3.8 Adverse Events of Special Interest**

An adverse event of special interest (AESI) is an event of scientific and medical interest towards improving the understanding of the IP. An AESI may be serious or non-serious. For this study, AESIs include:

1. Anaphylactic reactions
2. Immune complex disease (Type III hypersensitivity reactions)
3. Malignancy
4. Helminth infections
5. Severe infections which are defined as:

Tezepelumab - D5180C00018

- SAEs or
  - Requiring treatment with systemic antiviral medications, intravenous antibiotics or medications for helminth parasitic infection or
  - Requiring a premature and permanent discontinuation of study drug
6. Injection site reactions
  7. Opportunistic infections
  8. Guillain-Barre Syndrome
  9. Adrenal crisis

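### SAP 8.1.6 adds an undisclosed condition, an investigator-marked category, to the protocol's definition of severe infection, so an unmarked qualifying infection drops out of that AESI count

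*SAP*

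**What the plan says.** Protocol 8.3.8 lists severe infections among its AESIs. The entry opens "Severe infections which are defined as" and gives three alternatives joined by 'or'. The first is that the infection is an SAE. The second reads "Requiring treatment with systemic antiviral medications, intravenous antibiotics or medications for helminth parasitic infection or", and the third "Requiring a premature and permanent discontinuation of study drug". Any one is enough, and no investigator-assigned category is mentioned.

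SAP 8.1.6 carries a heading that presents its rule as the protocol's. It states: "Severe infections will use an investigator-driven definition, i.e. will be directly determined from what is entered on the eCRF". An event must have "AE Category' on Adverse Events eCRF page marked as 'Severe Infection" and, joined by an underlined 'and', must meet at least one of three criteria. These are "AE is serious ('Serious' on Adverse Events eCRF page marked as 'Yes'), or" the specified-treatment criterion, or "AE resulted in permanent discontinuation of study drug". The first and third name an AE-page field; the treatment criterion names none.

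Three other places bear on this:

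- SAP Section 1 says that changes from the protocol are described in Section 6. Section 6 lists only the new LTE analysis set.
- SAP 8.1 leaves detailed definitions for 8.1.1, 8.1.4, 8.1.8 and 8.1.9 to be finalised before primary lock. Section 8.1.6 is not among them.
- Protocol 8.3.4 lists the variables collected for each AE. An AE category is not one of them.

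**The concern.** The SAP rule looks like the protocol rule but contains an extra necessary condition. A pneumonia that leads to hospital admission, recorded as serious but with the category left unmarked, is a severe infection under the protocol and is not one under the SAP. Because the heading claims agreement and Section 6 is silent, a reader of the study report would take the tabulated rate to be the protocol-defined rate.

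Protocol 9.4.2 makes AESIs part of the assessment of the primary objective. The severe-infection definition feeds the AESI tables by SOC and PT, the causality tables, the exposure adjusted occurrence rates and the All Tezepelumab summary (SAP 4.5.1 and Table 10). Infection also has a mechanistic rationale here. Protocol 2.3 notes that "TSLP suppression could theoretically have unanticipated immune-related side effects impairing host defense against certain infections", although it goes on to say that no clear evidence supports such a role and that no infection signal has been seen.

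**Working it through.** The plan gives no figure for this AESI, so the check compares the two rules.

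**Inputs.** For an event that is an infection, let S = serious, T = needed one of the listed treatments, D = led to permanent discontinuation of IP, and M = category marked.

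- Protocol 8.3.8: infection and (S or T or D).
- SAP 8.1.6: M and (S or T or D).

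**Comparison.** S, T and D give 2 × 2 × 2 = 8 combinations, of which 8 − 1 = 7 meet at least one criterion.

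| Combinations of S, T, D | Protocol | SAP, marked | SAP, unmarked |
|---|---|---|---|
| 7 with a criterion met | counted | counted | not counted |
| 1 with none met | not counted | not counted | not counted |

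With the category marked, the rules agree in all 8. With it unmarked, the protocol counts 7 and the SAP counts 0. These are logical cells, not expected frequencies. They show the direction only: among infections, the extra condition can remove protocol-qualifying cases and cannot add any.

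**Where an unmarked qualifying infection still appears** (SAP 4.5.1):

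- If serious, in the SAE table by SOC and PT.
- If it stopped IP, in the DAE table by SOC and PT.
- If it qualifies by treatment alone, only in the general AE tables, unless it also meets the separate helminth or opportunistic infection AESI.

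**Size.** SAP 3.2.2 defines the exposure adjusted incidence rate as subjects with the event divided by the treatment group's total exposure. The denominator does not depend on how events are classified. If N subjects have a protocol-qualifying infection, exposure is E, and a share s of those subjects have at least one marked qualifying event, then:

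- protocol rate = N/E
- SAP rate = sN/E
- relative shortfall = 1 − s

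The documents give no value for s. As assumptions:

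| s | Shortfall |
|---|---|
| 1.00 | 0% |
| 0.95 | 5% |
| 0.90 | 10% |
| 0.80 | 20% |

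If s is the same in both arms, it cancels from the rate ratio, and the rate difference is multiplied by s.

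**The case against.** The strongest reply is that the protocol says which infections are severe but not how an AE is recognised as an infection. Some marker is needed, and the SAP openly chooses the investigator's entry, as it does for helminth infections (8.1.5) and injection site reactions (8.1.7). If site instructions say to mark the category whenever a criterion is met, the two rules coincide. Those instructions are not in the documents, so no actual loss can be shown.

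This stands as a limit on the harm. It does not make the rule the protocol's: the SAP neither cites such instructions nor provides a check on the marking.

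A reader might infer more than the documents support:

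- **That the rate is a known percentage too low.** The 5% to 20% figures only restate an assumed completeness of marking, and the loss may be nil.
- **That serious infections would go unreported.** They remain in the SAE tables, and those that stopped IP in the DAE tables. The AE and SAE rates named as the primary outcome do not use this definition.
- **That seriousness and discontinuation need no marker.** Neither field shows that an event is an infection.
- **That the comparison between arms is biased.** Investigators stay blinded (Protocol 6.3), so different marking by arm is not an obvious risk.
- **That sites will confuse severe with serious.** Protocol 8.3.8 defines the term for them, and Appendix B 6 warns of the distinction. Confusion is possible but not shown.

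**Conclusion.** The point holds as a difference between definitions. SAP 8.1.6 adds a necessary condition that Protocol 8.3.8 does not contain, presents the result as the protocol definition, and does not disclose it in Section 6. For infections the effect can only be to leave qualifying cases out of the severe-infection AESI tables. Those that qualify by treatment alone are the least visible, because neither the SAE nor the DAE table picks them up.

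The number left out cannot be determined from the documents. It is zero if marking is complete; otherwise the AESI rate falls in proportion to the share unmarked. Whether any case is lost rests on eCRF instructions and data checks that are not available here. The change is still worth making, because it is cheap and brings the count closer to the definition the SAP claims to use.

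**What to change.** Define the AESI as an AE that is **either** marked Severe Infection **or** coded to the MedDRA SOC Infections and infestations, **and** that is serious, or led to permanent discontinuation of IP, or required one of the listed treatments. Using either marker matters: relying on the SOC alone would drop events that the investigator marked but that code elsewhere.

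- Apply the seriousness and discontinuation criteria by program from the AE-page fields already named in SAP 8.1.6.
- For the treatment criterion, reconcile unmarked infections against concomitant medications by blinded review or site query before primary database lock. A program alone may not suffice: Protocol 6.5 lists reason for use and dates but not route, so it is not shown that intravenous antibiotics can be identified from the data.
- Keep the investigator-marked version as a comparison row.
- If the marked-only rule is retained as the main definition, list it in SAP Section 6 as narrower than the protocol's. If the SAP can no longer be amended, add the analysis and report the departure in the study report, as Protocol 9.4 provides.

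The cost is a little more programming and a review before lock. The reported severe-infection rate may be slightly higher.
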